4. SUBJECT DISPOSITION

4.1. Subject Enrollment and Disposition

A summary of subject enrollment will be provided by treatment group for each country, investigator within a country, and overall. The summary will present the number and percentage of subjects in the Safety Analysis Set. For each column, the denominator for the percentage calculation will be the total number of subjects analyzed for that column.

A summary of subject disposition will be provided by treatment group. This summary will present the number of subjects screened, the number of subjects enrolled, the number of subjects enrolled but never treated, and the number and percentage of subjects in each of the categories listed below. For the “Treated” category, the denominator for the percentage calculation will be the total number of subjects enrolled for each column. For all other categories, the denominator for the percentage calculation will be the total number of subjects in the Safety Analysis Set for each column.

- Treated (Safety Analysis Set)
- In FAS
- In PK Analysis Set
- Completed study treatment
- Did not complete study treatment with reasons for premature discontinuation of study treatment
- Completed the study
- Did not complete the study with reason for premature discontinuation of study

Among subjects who completed study treatment and who discontinued study treatment, the number and percentage of subjects will be summarized for:

- Who had no HCV posttreatment Week 4 assessment and thereafter (No HCV FU-4 and thereafter)
- Who had HCV posttreatment Week 4 assessment but no HCV posttreatment Week 12 assessment and thereafter (With HCV FU-4 but No FU-12 and thereafter)

If a subject did not have any HCV RNA assessment ≥ 21 days after the last dose of any study drug (ie, lower bound of FU-4 visit for HCV RNA data), the subject is categorized as having “No HCV FU-4 and thereafter”. If a subject had the HCV FU-4 assessment but did not have any HCV RNA assessment ≥ 70 days after the last dose of any study drug (ie, lower bound of FU-12 visit for HCV RNA data), the subject is categorized as having “With HCV FU-4 but No FU-12 and thereafter”.

In addition, the total number of subjects who were enrolled, and the number of subjects in each of the disposition categories listed above will be displayed in a flowchart.

The following by-subject listings will be provided by subject ID number in ascending order to support the above summary tables:

- Disposition of subjects who complete study treatment and study
- Disposition of subjects who did not complete study treatment and/or study with reasons for premature discontinuation of study drug and/or study
- Lot number and kit ID (if applicable)

4.2. Extent of Exposure

Extent of exposure to study regimen and individual study drug will be examined by assessing the total durations of study regimen and individual study drug exposure and the level of adherence to any study drug and individual study drug specified in the protocol.

4.2.1. Durations of Exposure to Study Regimen and Individual Study Drug

Total duration of exposure to study regimen will be defined as last dose date of any study drug minus first dose date of any study drug plus 1, regardless of any temporary interruptions in study drug administration, and will be expressed in weeks using up to 1 decimal place (e.g. 4.5 weeks). Total duration of exposure to individual study drug will be defined as last dose date of individual study drug minus first dose date of individual study drug plus 1, regardless of any temporary interruptions in study drug administration.

The total durations of exposure to study regimen and individual study drug will be summarized using descriptive statistics (n, mean, SD, median, Q1, Q3, minimum, and maximum) and using the number (ie, cumulative counts) and percentage of subjects exposed through the following time periods: Baseline (Day 1), Week 1 (Day 7), Week 2 (Day 14), Week 4 (Day 28), Week 8 (Day 56), and Week 12 (Day 84) for all subjects and additionally Week 16 (Day 112), Week 20 (Day 140), and Week 24 (Day 168) for subjects receiving 24 weeks of treatment. A 3-day window is applied to the last planned on-treatment visit to match with the protocol-specified visit window. Summaries will be provided by treatment group for the Safety Analysis Set.

4.2.2. Adherence to Study Drug

The level of adherence to individual study drug will be assessed separately based on the total amount of individual study drug administered relative to the total amount of individual study drug prescribed. In this study, LDV/SOF FDC 90/400 mg tablets, LDV/SOF FDC 22.5/100 mg tablets, and LDV/SOF 11.25/50 mg packets containing granules have been used. For RBV, both REBETOL capsules and REBETOL RBV oral solution could be used. Each capsule contains 200 mg RBV and the oral solution contains 40 mg RBV per mL.

Given the fact that multiple formulations of the study drug have been used in this study, the adherence will be calculated based on the amount of LDV/SOF FDC (mg) or RBV (mg) by the following formula:

$$\text{Level of Adherence(\%)} = \left(\frac{\text{Total Amount of Study Drug Administered}}{\text{Total Amount of Study Drug Prescribed at baseline}} \right) \times 100$$

Where the presumed total amount of study drug (mg) administered to a subject will be determined by the data collected on the drug accountability eCRF using the following formula:

$$\text{Total Amount of Study Drug (mg) Administered} = (\sum \text{Total Amount of Study Drug (mg) Dispensed}) - (\sum \text{Total Amount of Study Drug (mg) Returned})$$

Note: If calculated adherence is greater than 100%, the result will be set to 100%.

The total amount of prescribed LDV/SOF FDC (mg) for 12 weeks and 24 weeks are as follows:

Age Group and Body Weight	LDV/SOF Daily Dose	Total Amount of LDV/SOF Prescribed for 12 Weeks	Total Amount of LDV/SOF Prescribed for 24 Weeks
12 to <18 years any weight	490 mg/day	41160 mg	N/A*
6 to <12 years any weight	245 mg/day	20580 mg	41160 mg
3 to <6 years weighing ≥17 kg	245 mg/day	20580 mg	N/A*
3 to <6 years weighing <17 kg	183.75 mg/day	15435 mg	N/A*

*Note: No subject 12 to <18 or 3 to <6 years old was assigned to 24 weeks of treatment.

For subjects infected with HCV GT3, RBV was prescribed by weight at baseline. The total amount of RBV (mg) prescribed for 24 weeks is as follows:

Body Weight kg (lbs.)	RBV Daily Dose	RBV Number of Capsules	Total Amount of RBV Prescribed for 24 Weeks
<47 (<103)	15 mg/kg/day	Use Oral Solution. Divided dose in the morning and evening.	2,520 mg/kg
47-49 (103-108)	600 mg/day	1 × 200-mg capsules A.M. 2 × 200-mg capsules P.M.	504 capsules (100800 mg)
50-65 (110 – 143)	800 mg/day	2 × 200-mg capsules A.M. 2 × 200-mg capsules P.M.	672 capsules (134400 mg)
66-80 (145 – 176)	1000 mg/day	2 × 200-mg capsules A.M. 3 × 200-mg capsules P.M.	840 capsules (168000 mg)
81-105 (178- 231)	1200 mg/day	3 × 200-mg capsules A.M. 3 × 200-mg capsules P.M.	1,008 capsules (201600 mg)
>105 (>231)	1400 mg/day	3 × 200-mg capsules A.M. 4 × 200-mg capsules P.M.	1,176 capsules (235200 mg)

Note: Subjects with a body weight greater than or equal to 47 kg may utilize the RBV oral solution if necessary.

Weight reported as a decimal number was rounded to the whole number to determine the prescribed RBV dosage. For example, a subject weighing 49.5 kg fell into the 50-65 kg category and received 800 mg/day.

Subjects who prematurely discontinue study drug for lack of efficacy (ie, virologic failure) will have the total amount of study drug prescribed calculated up to the first date when virologic failure criteria were met. For virologic failure confirmed by 2 consecutive measurements the date of the first measurement will be used. If there are study drug bottles dispensed on or after the subject first met virologic failure criteria, these bottles will not be included in the calculation of adherence. If a bottle is dispensed and the bottle is returned empty, then the number of tablets returned will be entered as zero. If a bottle is dispensed but not returned (missing), the number of tablets taken from that bottle will be counted as zero.

Descriptive statistics for the level of adherence (n, mean, SD, median, Q1, Q3, minimum, and maximum) with the number and percentage of subjects belonging to adherence categories (e.g. < 80%, ≥ 80 to < 90%, ≥ 90%) will be provided by treatment group for the Safety Analysis Set. No inferential statistics will be provided for duration of exposure and adherence to study drug. Categorical displays will be provided for the number of subjects who are at least 80% adherent to individual study drug and study regimen (ie, adherence is ≥ 80% for each of the study drugs). No inferential statistics will be provided.

A separate by-subject listing of study drug administration and drug accountability will be provided by subject ID number (in ascending order) and visit (in chronological order).

4.3. Protocol Deviations

A summary of important protocol deviations will be provided by the Clinical Operations group for subjects in the Safety Analysis Set.

Subjects who received study drug other than their enrolled treatment assignment will be listed with the start and stop dates that they received incorrect study treatment.

5. BASELINE CHARACTERISTICS

5.1. Demographics

Subject demographic variables (ie, age, sex, race, and ethnicity) will be summarized by treatment group and total in each age group using descriptive statistics (n, mean, SD, median, Q1, Q3, minimum, and maximum) for age, and using the numbers and percentages of subjects for sex, race, and ethnicity. Age is calculated in years at the date of initial study drug administration. If a subject did not receive study drug after enrollment, the subject's age will be calculated from the date that the subject signed the informed consent form. The summary of demographic data will be provided for the Safety Analysis Set.

In addition, for subjects 3 to < 6 years of age, demographic variables (ie, age, sex, race, and ethnicity) will be summarized by treatment group as defined in [Table 3-3](#) and total.

A by-subject demographic listing will be provided by subject ID number in ascending order.

5.2. Other Baseline Characteristics

Other baseline characteristics include:

- weight in kg
- height in cm
- body mass index (BMI; in kg/m²)
- HCV genotype (genotype 1 [further broken down to 1a, 1b, and other], genotype 3, genotype 4, and other as applicable)
- cirrhosis (presence, absence, unknown)
- IL28B (CC, CT, TT)
- baseline HCV RNA (log₁₀ IU/mL) as a continuous variable and as categories (< 800,000 IU/mL, ≥ 800,000 IU/mL)
- baseline ALT (U/L) as a continuous variable and as categories (≤1.5 × ULN, > 1.5 × ULN)
- estimated glomerular filtration rate (eGFR) using Schwartz Formula (mL/min/1.73m²)
- prior treatment experience (treatment naïve, treatment experienced)
- IFN eligibility (IFN-eligible, IFN-ineligible)

- most recent response to prior HCV treatment (non-response, relapse/breakthrough, IFN-intolerant) for treatment experienced subjects
- mode of HCV Infection
- bone age in years
- Tanner Stage

Estimated Glomerular Filtration Rate (GFR) will be calculated using Schwartz Formula ($\text{mL}/\text{min}/1.73\text{m}^2 = k \times L/\text{Scr}$ [(k is a proportionality constant, for adolescent females ≥ 12 years old is 0.55; for adolescent males ≥ 12 years old is 0.70, and for children 3- <12 years old is 0.55); L is height in centimeters (cm); and Scr is serum creatinine (mg/dL)]

These baseline characteristics will be summarized by treatment group and total in each age group using descriptive statistics (n, mean, SD, median, Q1, Q3, minimum, and maximum) for continuous variables and using the numbers and percentages of subjects for categorical variables. The summary of baseline characteristics will be provided for the Safety Analysis Set.

In addition, for subjects 3 to < 6 years of age, baseline characteristics will be summarized by treatment group as defined in [Table 3-3](#) and total.

A by-subject listing of other baseline characteristics will be provided by subject ID number in ascending order.

[figure not shown]

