1. INTRODUCTION

1.1. Background

Hepatitis C virus (HCV) is responsible for a large proportion of chronic liver disease worldwide and accounts for 70% of cases of chronic hepatitis in industrialized countries. The global prevalence of chronic hepatitis C is estimated to average 3% {[Esteban 2008](#)}.

The natural history of chronic HCV-infection in children differs from that in adults since HCV-infection in children is relatively benign. Most children chronically infected with HCV are asymptomatic or have mild nonspecific symptoms. Clinical symptoms are present in approximately 20% of children in the first 4 years of life, with hepatomegaly being the most frequent sign (10%). Many, but not all, perinatally infected children will have intermittently or persistently abnormal alanine aminotransferase (ALT) or aspartate aminotransferase (AST) levels, particularly in the first 2 years of life. In children with vertical HCV-infection who have undergone liver biopsy, the histological spectrum is usually mild, although severe liver disease is encountered {[Mohan 2010](#)}. Despite the overall more favorable prognosis compared to adults, approximately 4% to 6% of children with chronic HCV-infection have evidence of advanced fibrosis or cirrhosis and some children eventually require liver transplantation for end-stage liver disease as a consequence of HCV-infection {[Hu 2010](#)}.

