3.1.2. Treatment Phase

The Treatment Phase will be initiated sequentially by age group as defined in Cohort 1, 2, and 3 of the PK Lead-in. Subjects who participated in PK Lead-in phase will immediately rollover into Treatment Phase with no interruption of study drug administration until the appropriateness of the dose has been confirmed by PK and safety results from the PK Lead-in. The first visit in the Treatment Phase for these subjects will be the Week 2 visit. Additional subjects will be enrolled in the Treatment Phase of each Cohort upon confirmation of the appropriateness of the dose from the PK Lead-in.

Children aged 3 to < 12 years (Group 2) and adolescents aged 12 to < 18 years (Group 1) with chronic HCV-infection and a HCV RNA \geq 1000 IU/mL at study entry (those who were dosed in the PK Lead-in phase will have met this criteria prior to enrollment) will be evaluated.

Subjects enrolled in the Treatment Phase will receive the following regimen:

a) United Kingdom:

- GT-1, GT-4, GT-5, & GT-6 treatment-naïve subjects with or without cirrhosis: LDV/SOF FDC for 12 weeks
- GT-1, GT-4, GT-5, & GT-6 treatment-experienced subjects without cirrhosis: LDV/SOF FDC for 12 weeks
- GT-1, GT-4, GT-5, & GT-6 treatment-experienced subjects with cirrhosis: LDV/SOF FDC for 24 weeks
- GT-3 treatment-experienced subjects with or without cirrhosis: LDV/SOF FDC + RBV for 24 weeks

b) United States/Australia/New Zealand:

- GT-1 treatment-naïve subjects with or without cirrhosis: LDV/SOF FDC for 12 weeks
- GT-1 treatment-experienced subjects without cirrhosis: LDV/SOF FDC for 12 weeks
- GT-1 treatment-experienced subjects with cirrhosis: LDV/SOF FDC for 24 weeks
- GT-4, GT-5, & GT-6 treatment-naïve or treatment-experienced subjects with or without cirrhosis: LDV/SOF FDC for 12 weeks

Table 3-1. Subject Enrollment by HCV Genotype, Country, and Treatment Duration

	GT-1			GT-3	GT-4, GT-5, & GT-6		
	Cirrhotic or Non-cirrhotic Subjects (TN)	Non-cirrhotic Subjects (TE)	Cirrhotic Subjects (TE)	Non-cirrhotic or Cirrhotic Subjects (TE)	Cirrhotic or Non-cirrhotic Subjects (TN)	Non-cirrhotic Subjects (TE)	Cirrhotic Subjects (TE)
United States	12 Weeks of treatment with LDV/SOF FDC	12 Weeks of treatment with LDV/SOF FDC	24 Weeks of treatment with LDV/SOF FDC	N/A	12 Weeks of treatment with LDV/SOF FDC	12 Weeks of treatment with LDV/SOF FDC	12 Weeks of treatment with LDV/SOF FDC

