6.2. Screening Assessments

6.2.1. Screening Visit (Day -28 to Day 0)

Subjects will complete all screening assessments within 28 days of the Day 1 visit. The screening window can be extended to 42 days for subjects requiring additional HCV GT testing or for extenuating circumstances.

The following procedures will be performed and documented:

- Written informed consent from parent or legal guardian and assent from subject, if applicable (see above)
- Medical history, including:
 - Hepatitis C history
 - Hepatitis C treatment history
 - Family history (including height of parents, if known)
 - Liver biopsy results (if available)
- Complete physical examination
- Vital signs (temperature, blood pressure, pulse, respiratory rate) and body weight and height

- Obtain blood samples for tests as listed in Section 6.6.1:
 - Hematology
 - Chemistry
 - Coagulation tests
 - HCV RNA
 - Determination of HCV viral GT and subtype
 - HCV antibody, HIV 1/2 antibody, HBV surface antigen (HBsAg), HBV surface antibody (HBsAb), HBV core antibody (HBcAb), and HAV antibody
 - HbA_{1c}
 - TSH
 - IL28B
 - Serum β -hCG pregnancy test for females of childbearing potential only
 - Alpha fetoprotein (AFP)
 - Alpha-1 anti-trypsin (ATT)
- Obtain urine sample for:
 - Urinalysis
 - Urine Drug Screen
- Review of concomitant medications
- Ask subject and/or parent/legal guardian if the subject is able to swallow and tolerate taking pills.
- Review of all inclusion and exclusion criteria
- Perform LDV/SOF FDC swallowability assessment, as applicable

Subjects meeting all of the inclusion criteria and none of the exclusion criteria will return to the clinic for the Day 1 visit assessments.

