3.2. Subject Grouping

For analyses based on the All Enrolled Analysis Set or FAS, subjects will be grouped according to the treatment to which they were enrolled. For analyses based on the Safety Analysis Set, subjects will be grouped according to the actual treatment received. The actual treatment received is defined as the enrolled treatment except for subjects who received treatment that differs from the enrolled treatment for the entire treatment duration. In this case, the actual treatment received is defined as the treatment received for the entire treatment duration.

Generally, subjects are analyzed, except for the safety analysis, by treatment groups based on age group, HCV genotype, prior treatment experience, cirrhosis status, and treatment duration:

Table 3-1. Non-safety Treatment Groups*

12 to < 18 Years Old		3 to < 12 Years Old			
LDV/SOF (90/400 mg) 12 Weeks		LDV/SOF (45/200 mg or 33.75/150 mg) 12 Weeks		LDV/SOF (45/200 mg) 24 Weeks	LDV/SOF+RBV (45/200 mg) 24 Weeks
GT1 TN w/ or w/o cirrhosis (N =)	GT1 TE without cirrhosis (N =)	GT1, GT4 TN w/ or w/o cirrhosis (N =)	GT1 TE without cirrhosis (N =)	GT1 TE with cirrhosis (N =)	GT3 TE w/ or w/o cirrhosis (N =)
6 to < 12 Years Old			3 to < 6 Years Old		
LDV/SOF (45/200 mg) 12 Weeks		LDV/SOF (45/200 mg) 24 Weeks	LDV/SOF+RBV (45/200 mg) 24Weeks	LDV/SOF (45/200 mg or 33.75/150 mg) 12 Weeks	
GT1, GT4 TN w/ or w/o cirrhosis (N =)	GT1 TE without cirrhosis (N =)	GT1 TE with cirrhosis (N =)	GT3 TE w/ or w/o cirrhosis (N =)	GT1, GT4 TN w/ or w/o cirrhosis (N =)	

GT = genotype, TN = Treatment Naïve, TE = Treatment Experienced, w/ = with, w/o = without
 *Treatment Groups reflect the subjects actually enrolled.

For the safety analysis, subjects will be analyzed by the following groups based on age group, treatment regimen and duration:

Table 3-2. Safety Treatment Groups

12 to < 18 Years Old	3 to < 12 Years Old		
LDV/SOF (90/400 mg) 12 Weeks (N =)	LDV/SOF (45/200 mg or 33.75/150 mg) 12 Weeks (N =)	LDV/SOF (45/200 mg) 24 Weeks (N =)	LDV/SOF+RBV (45/200 mg) 24 Weeks (N =)
6 to < 12 Years Old			3 to < 6 Years Old
LDV/SOF (45/200 mg) 12 Weeks (N =)	LDV/SOF (45/200 mg) 24 Weeks (N =)	LDV/SOF+RBV (45/200 mg) 24 Weeks (N =)	LDV/SOF (45/200 mg or 33.75/150 mg) 12 Weeks (N =)

Subjects in the 3 to < 6 years of age group will have additional selected efficacy and safety analyses performed according to baseline weight in the following subgroups:

Table 3-3. Subgroups for Selected Analyses in 3 to < 6 years of Age

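### Treatment-experienced GT-1 children of unknown cirrhosis status on 12 weeks can only be reported as without cirrhosis, and the SVR12 subgroup that would separate them is missing from the SAP

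*SAP*

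**What the plan says.** **Duration.** Protocol 3.1.2 splits GT-1 TE subjects by cirrhosis in every country. The US, Australia and New Zealand lines read "GT-1 treatment-experienced subjects without cirrhosis: LDV/SOF FDC for 12 weeks" and "GT-1 treatment-experienced subjects with cirrhosis: LDV/SOF FDC for 24 weeks", and the UK list applies the same split to GT-1, GT-4, GT-5 and GT-6. Elsewhere in that section cirrhosis makes no difference. UK GT-3 is "GT-3 treatment-experienced subjects with or without cirrhosis: LDV/SOF FDC + RBV for 24 weeks". The GT-4/5/6 line outside the UK ends "treatment-experienced subjects with or without cirrhosis: LDV/SOF FDC for 12 weeks". Treatment-naïve (TN) subjects get 12 weeks whatever their status. SAP Table 1-1 repeats this scheme.

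**Establishing status.** The screening list in Protocol 6.2.1 includes, under medical history, "Liver biopsy results (if available". It lists no fibrosis test. Protocol 4.3 names biopsy as the method for cirrhosis, but only in an exclusion that applies to the PK Lead-in.

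**Analysis.** SAP 5.2 records "cirrhosis (presence, absence, unknown" as a baseline characteristic, summarised by treatment group. SAP Table 3-1 heads its only 12-week TE column, in each age group that has one, "GT1 TE without cirrhosis (N". The TN columns pool over cirrhosis status. SAP 6.1.2 gives SVR12 with a Clopper-Pearson interval by treatment group and in total for each age group.

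**Subgroups.** Protocol 9.6.3 commits to SVR12 by treatment experience and cirrhosis status. The subset list in SAP 3.4 does not contain cirrhosis status, and SAP 6.4 states that nothing was changed from the protocol's efficacy analyses.

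**The concern.** The regimen lists and the TE columns of Table 3-1 treat cirrhosis in GT-1 TE subjects as a yes/no fact. The baseline table treats it as something that may not be known. Nothing connects the two: no rule says how status is established in the Treatment Phase, how a GT-1 TE child of unknown status is given a duration, or which Table 3-1 column that child joins.

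What is at stake is whom the result describes. SVR12 in the 12-week TE column will be read as the response to 12 weeks in previously treated children without cirrhosis. If the column mixes documented absence with undetermined status, the heading says more than the data do. A reader could then see the number of unknowns in the baseline table but could not obtain SVR12 for the children whose status was established.

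**Working it through.** The plan states no figure on this point. Its only precision figures, 5.9 and 5.4 percentage points, are for whole age groups. They reproduce as 1.96 × √(0.9 × 0.1/100) = 5.88 points and 1.96 × √(0.9 × 0.1/120) = 5.37 points, and do not bear on the issue. The check is therefore mainly a trace through the tables.

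**Step 1: where cirrhosis changes the duration** (Protocol 3.1.2 and Table 3-1; SAP Table 1-1).

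| Subjects | Cirrhosis changes duration? |
|---|---|
| TN, GT-1/4/5/6, all countries | No, 12 weeks |
| TE, GT-1, all countries | Yes, 12 or 24 weeks |
| TE, GT-4/5/6, UK | Yes, 12 or 24 weeks |
| TE, GT-4/5/6, US/Australia/New Zealand | No, 12 weeks |
| TE, GT-3, UK | No, 24 weeks |

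TE enrolment is capped at 40 of about 220, so at least 220 − 40 = 180 subjects (180/220 = 82%) are TN and unaffected.

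**Step 2: where a TE child of unknown status lands.** Table 3-1 reflects actual enrolment and has no GT-4/5/6 TE column, so in the analysis the issue is confined to GT-1 TE. On 12 weeks, the only TE column is the one headed without cirrhosis. On 24 weeks, the only GT-1 TE column is the one headed with cirrhosis. For ages 12 to < 18 there is no choice at all: Table 3-1 has a single TE column, and SAP 4.2.2 notes that nobody of that age was assigned 24 weeks. The 3 to < 6 table has TN subjects only.

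**Step 3: what the planned outputs show.** The baseline summary (SAP 5.2) gives the number unknown in each treatment group. The SVR12 tables (SAP 6.1.2, 6.1.3) give one rate for each column and for each SAP 3.4 subset. None of those subsets is cirrhosis status, so no planned table gives SVR12 for the unknowns, or for documented absence, on its own.

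**Step 4: size.** Let *m* be the number of GT-1 TE children of unknown status in the 12-week column, and *p* the chance that one has advanced fibrosis or cirrhosis. Protocol 1.1 says "approximately 4% to 6% of children with chronic HCV-infection have evidence of advanced fibrosis or cirrhosis", so *p* = 0.04 to 0.06, assumed here to apply to TE children. The documents do not give *m*. The expected number is *m* × *p*; the chance of at least one is 1 − (1 − *p*)^*m*.

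| *m* (assumed) | Expected number | Chance of at least one |
|---|---|---|
| 10 | 10 × 0.04 = 0.4 to 10 × 0.06 = 0.6 | 1 − 0.96^10 = 34% to 1 − 0.94^10 = 46% |
| 20 | 0.8 to 1.2 | 56% to 71% |
| 40 (cap) | 1.6 to 2.4 | 80% to 92% |

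The last row is an upper bound. The cap covers all TE subjects, so the column would not reach 40 if the GT-1 TE with cirrhosis and GT-3 TE columns hold anyone. The rate also counts advanced fibrosis, which probably overstates cirrhosis alone.

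**The case against.** The case for leaving the plan alone has real weight.

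- **The count is already visible.** SAP 5.2 summarises cirrhosis by treatment group and lists it by subject. This stands: the number unknown is not hidden. What is missing is SVR12 by status.
- **No affected child is shown to exist.** The unknown level covers all subjects, most of whom are TN, and the documents are equally consistent with every unknown being TN. This stands, and is why the relabelling below is conditional.
- **Table 3-1 already crosses treatment experience with cirrhosis for GT-1 TE.** Only in part: it has no unknown level, and its TN columns pool over status, so it does not deliver the Protocol 9.6.3 subgroup.
- **Any bias would probably run the other way.** The protocol gives GT-1 TE children with cirrhosis a longer course. On that logic, an undetected case on 12 weeks would tend to lower SVR12 in the column. That is fair, and the point here is about whom the rate describes, not about inflation.
- **Efficacy is secondary and descriptive.** True, which limits the severity. It does not make the heading accurate.

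A reader might infer two stronger things. One is that cirrhosis can be known only from a biopsy. The documents do not say so: the biopsy wording in Protocol 4.3 is limited to the PK Lead-in, which admits only TN children, and screening also takes hepatitis C history. The supportable statement is that no other method is named. The other is that children of unknown status in general are analysed as non-cirrhotic. No sentence says this, TN children of unknown status fall in pooled columns, and the conclusion follows only for GT-1 TE children on 12 weeks.

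**Conclusion.** The point holds in a limited form. For GT-1 TE subjects the regimen lists and Table 3-1 recognise two cirrhosis states where SAP 5.2 recognises three. A 12-week GT-1 TE child of unknown status has nowhere to go but the column headed without cirrhosis. For UK GT-4/5/6 TE subjects the same gap exists in the regimen list, though Table 3-1 has no such column. Separately, the SAP drops a subgroup that Protocol 9.6.3 promises and reports no change; that mismatch needs no assumption about numbers.

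The likely effect on the SVR12 estimate is small: about 0.4 to 0.6 children with advanced fibrosis or cirrhosis if 10 were unknown, and 0.8 to 1.2 if 20 were. These figures rest on an assumed number of unknowns and on a background rate that is not specific to TE children. The labelling problem does not depend on either: one unknown child is enough to make the heading unsupported. The documents do not establish that any misclassification took place. This is worth correcting because it settles whom the 12-week TE result describes and uses data already collected.

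**What to change.** 1. In SAP Table 3-1, if the 12-week TE column contains any child of unknown status, head it *GT1 TE, cirrhosis absent or unknown*.
2. Add cirrhosis status (presence, absence, unknown) within treatment experience to the SAP 3.4 subsets, and report SVR12 with its Clopper-Pearson interval for each level. This also restores the Protocol 9.6.3 analysis and makes the statement in SAP 6.4 accurate on this item.
3. The clinical team should reconcile the regimen lists (Protocol 3.1.2, SAP Table 1-1) with the unknown category in SAP 5.2, and state how status was established in the Treatment Phase and how unknown status was handled for subjects whose duration depends on it. No regimen or diagnostic rule is proposed here.

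Items 1 and 2 cost a label and a few table rows and need no new data. The downside is small cells. Even if every child responded, the exact two-sided 95% lower limit is 0.025^(1/*m*): 0.025^(1/10) = 69% for 10 of 10 and 0.025^(1/20) = 83% for 20 of 20. The rows are therefore descriptive and should be read that way. Item 3 is a clarification of text.
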